A formal vanguard analysis, marking the end of the vanguard phase of the FLINT trial, will be performed approximately 65 weeks after the first patient is randomized. The analysis will be focused on interim efficacy outcomes and safety information using data from the estimated 25-40% of patients who will have completed at least 24 weeks of follow-up by the time of the interim analysis. Our pre-specified interim criterion for efficacy for continuing the FLINT trial beyond the vanguard phase is based on serum ALT: the criterion for continuation will be considered met if the upper 95% confidence limit on the between-group mean difference in mean changes from baseline to the 24 week measure of ALT, comparing the obeticholic acid versus placebo groups, is at least a 20% net reduction in serum ALT from the overall baseline mean ALT. The analysis will also include detailed safety data, as required by the DSMB, to determine whether any emergent safety issues are present. This vanguard safety analysis will consist of, but is not limited to, counts of adverse events (AEs) and serious adverse events (SAEs) by treatment group with associated P-values based on Fisher's exact tests or other tests, as appropriate. The final decision as to whether to continue the FLINT trial beyond the vanguard phase will be made by the NIDDK program official for the NASH CRN trial, which will be informed by any recommendations from the FLINT DSMB, taking the interim criterion for efficacy, safety, and other relevant information that may arise into account.

Interim analysis

The DSMB will review one planned interim analysis of the primary histological outcome measure. O'Brien-Fleming statistical stopping guidelines for efficacy will be applied. This interim efficacy analysis will occur when approximately 50% (140 of the 280 patients) have completed both baseline and 72 week biopsies. Based on the Lan-DeMets method for group sequential trials using O'Brien-Fleming boundaries (Reboussin et al., 2000), the levels of significance for the interim and final analyses will be $\alpha=0.00305$ and $\alpha=0.049$, respectively.

Sample size considerations

- Total of 280 patients in 2 groups of equal size (140 per group)
- Primary comparison: Obeticholic acid group vs. Placebo group
- Primary outcome measure: Histological improvement in NAFLD (defined above)
- Error protection: Type I = 0.05 and Type II = 0.10 (90% power)

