3.2 Treatment groups

Patients who have signed an informed consent statement and who meet the eligibility criteria will be randomly assigned to one of the two groups for 72 weeks of treatment:

Group 1: Obeticholic acid (25 mg daily as a capsule orally)

Group 2: Placebo (as an identical capsule as active drug)

The randomization scheme will assign patients in randomly permuted blocks of assignments stratified by presence of diabetes and clinical center; block size will be determined randomly. This scheme will ensure that the two groups will be balanced by calendar time of enrollment (to minimize secular effects), by clinic (to minimize clinic-specific effects of differences in patient populations and management), and by diabetes status.

The randomization plan will be prepared and administered centrally by the Data Coordinating Center (DCC) but will not require real time interaction with a DCC staff member. Requests for randomizations will be made by the clinics using a web-based application. An assignment will be issued only if the database shows that the patient is eligible, has signed the consent statement, and has had all required baseline data keyed into the database.

Drug administration

Obeticholic acid will be administered orally as a single capsule of 25 mg per day. An identical appearing placebo capsule will be taken daily by patients assigned to the placebo group. Patients will be instructed to take the medication at the same time each day to the extent that is practical, and they will be told not to take more than one dose in a day if they miss a dose.

Rationale for 25 mg daily dose of obeticholic acid

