4.1 Recruitment

Approximately 280 patients will be recruited from the eight clinical centers of the NASH CRN (averaging 35 patients per center) over an 18 month period. Eligible patients will be identified and recruited at the participating clinical centers subject to the inclusion and exclusion criteria. Clinics will be expected to recruit sufficient overall numbers of minorities and women so that results can be generalized to these populations. Each clinic will develop a recruitment plan. These plans will vary from clinic to clinic depending on the available pools of patients and local recruitment resources and referral patterns.

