7.2 Statistical analysis

Primary hypothesis

Statistical analyses for the primary hypothesis will follow the intention-to-treat paradigm, which means that all randomized patients with baseline and 72 week liver biopsies will be included in the treatment group to which they were assigned. Any randomized patient who does not have the requisite biopsies will be accounted for and compared by assigned treatment group. Patients not able to be included in the intention-to-treat analyses will be compared to those who are included with respect to demographic and other characteristics.

Since the primary outcome measure, defined in sections 3.4 and 6.1, is a binary indicator of improvement in histologic activity score after 72 weeks of treatment compared to baseline and since the randomization is stratified by clinic and diabetes status, P-values will be derived from the Mantel-Haenszel χ^2 test for stratified 2x2 tables. The proportion of patients improved in the group assigned to obeticholic acid will be compared to the group assigned to placebo and a two-tailed p-value of ≤ 0.05 will be considered statistically significant.

Stratification

Given the randomized design and adequate size planned for the FLINT trial, it is unlikely that confounding of the treatment groups by covariates related to the change in histologic activity score will occur. However, if confounding should occur, multivariate-adjusted logistic regression analyses with histologic improvement as the binary response and treatment group indicator and any suspected confounders as covariates will be carried out to determine the sensitivity of the primary P-value to confounding.

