7.5 Vanguard analysis

An unmasked vanguard analysis, using change in ALT (U/L) from baseline to the 24 week follow-up visit as the primary vanguard outcome, will be carried out for review by the DSMB in order to advise the NIDDK on whether the FLINT trial should continue. The vanguard design requires that the vanguard analysis and the decision to continue must be completed before any patient undergoes a 72 week end-of-study biopsy. This means that the vanguard analysis of ALT change must occur approximately 65 weeks after the first randomized patient is enrolled when between 70 (25% of total sample size) and 112 (40%) will have a 24 week ALT measure, but before the first patient (or any other patient) has undergone a 72 week liver biopsy.

The vanguard analysis statistical guideline indicating sufficient evidence that, compared to placebo, 24 weeks of treatment with obeticholic acid results in a greater reduction in ALT (BL – 24 weeks) will be considered met if the upper 95% confidence limit for the net percentage reduction in mean ALT (BL-24 weeks) in the obeticholic acid group vs. placebo group is greater than or equal to 20%. The net reduction and 95% upper confidence interval will be calculated from a multiple linear regression model with patient level changes in ALT (U/L) at baseline minus ALT (U/L) at 24 weeks as the response variable (y) and independent variables: obeticholic acid indicator ($x_1=1$, if obeticholic acid, 0, if placebo) and baseline ALT (U/L) (x_2): $E(y_i)=\beta_0+ \beta_1x_1+ \beta_2x_2+\epsilon_i$, $i=1,2,\dots,n$; n =number of patients in the vanguard analysis and ϵ_i are i.i.d. Gaussian($0,\sigma^2$).

The estimated between group (obeticholic acid vs. placebo) difference in mean change in ALT from BL

to 24 weeks is b_2 with 95% CI: $b_2 \pm t_{n-3} \widehat{\sigma}(b_2)$ where t_{n-3} is the 97.5th percentile of the t-distribution with $n-3$ degrees of freedom and $\widehat{\sigma}(b_2)$ is the estimated standard error of b_2 from the regression analysis. The estimated net reduction in ALT in the obeticholic acid group, expressed as percentage of the overall baseline mean ALT, \overline{ALT} , is $100 \times b_2 / \overline{ALT}$ with upper 95% confidence limit: $100 \times [b_2 + t_{n-3} \widehat{\sigma}(b_2)] / \overline{ALT}$. SAS PROC REG will be used to fit the regression model and calculate the upper 95% confidence limit to determine whether its value is a 20% or more net reduction in ALT.

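### The vanguard ALT model omits the randomization strata; if center or diabetes predicts ALT change, its standard error is conservative and the upper-limit rule becomes somewhat easier to meet

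*Protocol*

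**What the plan says.** Section 7.5 gives the vanguard model in full. The response is ALT at baseline minus ALT at 24 weeks, and the terms are "independent variables: obeticholic acid indicator ($x_1=1$, if obeticholic acid, 0, if placebo) and baseline ALT (U/L"). It also fixes the t quantile at n-3 degrees of freedom, which leaves room for no further covariate. The guideline is met if the upper 95% limit of the net percentage reduction is at least 20%. The analysis is expected when "between 70 (25% of total sample size) and 112 (40%) will have a 24 week ALT measure".

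The design is described in Section 3.2: "The randomization scheme will assign patients in randomly permuted blocks of assignments stratified by presence of diabetes and clinical center". The synopsis names the same two factors. Section 7.2 gives the reason for stratifying the primary Mantel-Haenszel test: "since the randomization is stratified by clinic and diabetes status". Section 4.1 sets the number of sites: "Approximately 280 patients will be recruited from the eight clinical centers of the NASH CRN".

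**The concern.** The protocol states a principle in Section 7.2, that the analysis should respect the randomization strata, and does not apply it to the one model that feeds the decision to continue. This is a fixed choice and not a detail left open, because the equation, the degrees of freedom and the software procedure are all given.

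Permuted blocks within center and diabetes make those factors roughly balanced between arms, so most of their variation drops out of the treatment contrast. A model without them still counts that variation in the residual. If they matter for ALT change, the reported standard error then exceeds the true one.

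In most settings that only costs power. Here the limit compared with 20% is the estimate plus t times the standard error, so an overstated standard error raises it and makes continuation easier. Section 3.3 says the vanguard design is there to protect patients from futile treatment and unneeded biopsies. Leniency works against that aim.

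**Working it through.** **Plan's own figure.** 0.25 × 280 = 70 and 0.40 × 280 = 112, as stated. The protocol gives no standard deviation, standard error, interval width or pass probability for the vanguard rule, so nothing else can be reproduced.

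**Inputs from the protocol.** n = 70 to 112; two equal arms ("Total of 280 patients in 2 groups of equal size (140 per group"); 8 centers; diabetes yes/no; two-sided 95% limit; threshold 20%.

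**Assumed.** Mean baseline ALT 80 U/L; residual SD after baseline ALT 40 U/L (50% of the mean); equally likely centers and diabetes levels; block sizes 2, 4 and 6. R² is the share of residual variance explained by center and diabetes, taken from 0 to 0.20. Section 7.5 attaches the limit to b_2, although treatment is x_1. I take the treatment coefficient to be intended.

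**Degrees of freedom.** Planned model: intercept, treatment, baseline ALT, so n-3 (67 or 109). Adding 1 diabetes and 7 center terms gives n-11 (59 or 101).

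**Half-width under exact balance.** Ratio adjusted/planned = [t(n-11)/t(n-3)] × √(1-R²).
- n = 70: t = 2.0010 v 1.9960. Ratio 1.0025 at R² = 0 and 0.897 at R² = 0.20.
- n = 112: t = 1.9837 v 1.9820. Ratio 1.0009 at R² = 0 and 0.895 at R² = 0.20.

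Exact balance is too optimistic. There are 8 × 2 = 16 strata, so 70/16 = 4.4 to 112/16 = 7 patients in each, and many blocks will be incomplete. I therefore simulated the stratified blocks, 4,000 trials per row, with no drug effect.

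| n | R² | Planned model: reported SE / actual SE (U/L) | Half-width, adjusted/planned | Guideline met, planned → adjusted |
|---|---|---|---|---|
| 70 | 0 | 9.61 / 9.59 | 1.019 | 62.8% → 63.7% |
| 70 | 0.05 | 9.61 / 9.27 | 0.992 | 63.6% → 62.2% |
| 70 | 0.10 | 9.63 / 9.27 | 0.965 | 63.7% → 60.6% |
| 70 | 0.20 | 9.63 / 8.74 | 0.910 | 64.3% → 57.0% |
| 112 | 0 | 7.57 / 7.46 | 1.007 | 44.2% → 44.8% |
| 112 | 0.05 | 7.58 / 7.45 | 0.980 | 43.9% → 42.5% |
| 112 | 0.10 | 7.58 / 7.13 | 0.954 | 44.3% → 40.6% |
| 112 | 0.20 | 7.59 / 7.08 | 0.900 | 45.6% → 36.9% |

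A second run at R² = 0.20 gave 63% → 55% (n = 70) and 45% → 36% (n = 112). The simulation standard error of one pass rate is about √(0.63 × 0.37/4000) = 0.8 points.

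**At a true 20% net reduction.** With a correct standard error the limit misses 20% only if the estimate falls more than t standard errors below the truth, which is 2.5%. Simulated pass rates, planned → adjusted:
- R² = 0: 97.6% → 97.4% (n = 70) and 96.8% → 96.4% (n = 112).
- R² = 0.10: 98.4% → 98.3% (n = 70) and 98.0% → 97.8% (n = 112).
- R² = 0.20, n = 112, exact balance: Φ(1.982/√0.8) = 98.7% against Φ(1.984) = 97.6%.

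**The upper-limit rule by itself.** SE = 2 × 40/√n and the threshold is 0.20 × 80 = 16 U/L.
- n = 70: SE 9.56, half-width 1.996 × 9.56 = 19.1 U/L, or 23.9% of 80. Chance of passing with no effect = 1 - Φ((16 - 19.1)/9.56) = 63%.
- n = 112: SE 7.56, half-width 15.0 U/L (18.7%). Chance of passing = 45%.
- Over SD 25 to 55 U/L this chance runs from 25% to 78% (n = 70) and from 8% to 67% (n = 112).

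**The case against.** The strongest reply is that nothing in the protocol shows center or diabetes to predict ALT change once baseline ALT is in the model. That stands. At R² = 0 the planned standard error is right (9.61 v 9.59 at n = 70), and adding the strata widens the interval by 0.7 to 1.9%. A reader might infer that the planned standard error simply is too large; the documents do not support that flat statement. They make an effect plausible. Section 3.2 stratifies by clinic because populations and management differ, Section 5.2 permits vitamin E and thiazolidinediones, and Section 2.5 reports that ALT improves over 3 to 6 months on vitamin E and on pioglitazone. They do not size it.

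Second, the shortcut SE × √(1-R²) overstates the gain. At R² = 0.20 it implies a reported standard error 1/√0.8 = 1.12 times the true one. The simulation gives 9.63/8.74 = 1.10 and 7.59/7.08 = 1.07. This stands too, so the simulated figures should be used.

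Third, the planned interval is valid, at worst conservative. The guideline is one input to a decision by the NIDDK program official, who also weighs safety and the DSMB's advice. That limits the consequence but does not remove the reason to model the strata.

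Fourth, a reader might extend the point to the adjusted logistic model in Section 7.2 and say that it drops the strata. It does not follow. That model is a contingent sensitivity analysis with "treatment group indicator and any suspected confounders as covariates", which does not exclude center or diabetes.

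**Conclusion.** The omission is a fact of the text and inconsistent with the protocol's own reasoning for the primary test. Its effect is conditional: the standard error is conservative, and the guideline easier to meet, only if center or diabetes predicts ALT change beyond baseline ALT.

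For 0 to 20% of residual variance explained, SD about 50% of mean ALT and n = 70 to 112, modelling the strata changes the interval width by about +2% to -10%. The pass rate under no drug effect changes by about +1 to -9 points, with little lost at a true 20% reduction. All of this rests on assumed values, since the protocol supplies neither the SD nor a stratum effect.

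It would go too far to say that the drug could pass because of center and diabetes noise. Comparing the upper limit with 20% already lets an inert drug through about 63% (n = 70) or 45% (n = 112) of the time at this SD with non-prognostic strata, and 37 to 57% still pass after adjustment at R² = 0.20. The strata are a secondary contributor. This is a modest improvement in efficiency and consistency that is worth making.

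**What to change.** In Section 7.5, add diabetes status (1 term) and clinical center (7 terms for 8 levels) to the regression, and use the t quantile with n-11 degrees of freedom for the limit. While that line is being edited, make the coefficient label agree with the model, since treatment is x_1 but the limit is written with b_2; that is a separate slip. No change to Section 7.2 is needed on this account.

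Both factors are known for every randomized patient, so no new data are required. The price is 8 degrees of freedom, which means an interval about 1 to 2% wider if the strata turn out not to be prognostic. The leniency of the upper-limit criterion needs its own review.

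### Section 7.5 writes the vanguard ALT formula with b_2, the baseline-ALT slope, where its own model makes b_1 the obeticholic acid effect

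*Protocol*

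**What the plan says.** Section 7.5 (Vanguard analysis) sets out the model in full. The response is "patient level changes in ALT (U/L) at baseline minus ALT (U/L) at 24 weeks as the response variable (y"), so a positive value is a fall in ALT. The two regressors are the "obeticholic acid indicator ($x_1=1$, if obeticholic acid, 0, if placebo) and baseline ALT (U/L) (x_2"). The model is "E(y_i)=\beta_0+ \beta_1x_1+ \beta_2x_2+\epsilon_i", numbered from an intercept β0.

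The next paragraph names the quantity of interest in words, "The estimated between group (obeticholic acid vs. placebo) difference in mean change in ALT from BL", and then states that this difference "to 24 weeks is b_2 with 95% CI". The interval uses the "estimated standard error of b_2 from the regression analysis". The net reduction is 100 × b_2 divided by mean baseline ALT, "expressed as percentage of the overall baseline mean ALT", and its upper limit is 100 × [b_2 + t·SE(b_2)] divided by the same mean. The guideline is met if that upper limit is 20% or more. The symbol b_2 occurs eight times in the paragraph; b_1 does not occur at all.

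The same criterion is described in words in the synopsis (Vanguard analysis), in section 3.3 and in the guideline sentence of section 7.5. Each time it is a comparison of the obeticholic acid group with the placebo group.

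**The concern.** The formula and the model that it draws on disagree. In that model b_1 is the adjusted treatment difference in U/L. b_2 says how much more ALT falls per additional U/L of baseline ALT, which is largely regression to the mean. It has no units, so dividing it by a mean in U/L does not give a percentage, and it does not measure the difference between the arms.

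This is the pre-specified efficacy guideline for continuing beyond the vanguard phase. It is computed on unmasked data, and no end-of-treatment biopsy may be done until the decision to continue is taken. A formula in that position should be executable as written. If it is not, the analyst must either follow a meaningless expression or depart from the written one with unmasked data in hand. The second course is sensible but leaves room for a later question about whether the rule was changed.

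**Working it through.** **Inputs from the protocol.** Response, regressors and model as in section 7.5; threshold 20%; critical value the 97.5th percentile of t with n − 3 degrees of freedom; n between 70 and 112; ALT above 300 U/L excluded (section 4.3).

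**Assumed inputs (not in the protocol).** Baseline ALT mean/SD of 50/25, 80/45 and 110/60 U/L; residual SD 0.5 × mean; true β2 of 0.3 and 0.7; true net reduction 0, 20 and 40%.

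**Figures that the protocol does give.** 25% and 40% of 280 are 70 and 112, as stated. n − 3 is right for three coefficients. The protocol states no probability of meeting the rule, so there is none to reproduce.

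**Step 1: which coefficient.** At a fixed baseline ALT, E(y) with x_1 = 1 minus E(y) with x_1 = 0 is (β0 + β1 + β2x_2) − (β0 + β2x_2) = β1. The treatment difference is β1 and β2 cancels.

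**Step 2: what the literal rule requires.** 100 × U/mean ≥ 20 means U ≥ 0.20 × mean, where U is the upper limit for b_2.

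| Mean ALT (U/L) | U needed | Result if U = 1 |
|---|---|---|
| 40 | 8 | 2.5% |
| 60 | 12 | 1.7% |
| 80 | 16 | 1.25% |
| 100 | 20 | 1.0% |
| 150 | 30 | 0.7% |

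A slope of this kind plausibly lies between 0 and 1. With U = 1 the rule needs a mean ALT of 5 U/L or less; with U = 2, 10 U/L or less.

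**Step 3: likely size of the literal limit.** Approximately SE(b_2) = residual SD / (SD of baseline × √n).
- Highest case (mean 50, slope 0.7, n = 70): SE = 25/(25 × 8.37) = 0.120; U = 0.7 + 1.996 × 0.120 = 0.94; 100 × 0.94/50 = 1.9%.
- Lowest case (mean 110, slope 0.3, n = 112): SE = 55/(60 × 10.58) = 0.087; U = 0.3 + 1.982 × 0.087 = 0.47; 100 × 0.47/110 = 0.43%.

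Simulating all 36 combinations (1,000 trials each) gave average limits of 0.4 to 1.9% and a maximum of 3.3%. The b_2 rule was met in 0% of trials, including those with a true 40% reduction. Making the drug effect proportional to baseline ALT, the case in which b_2 could pick up some treatment signal, also gave 0%, with a largest limit of 1.6%.

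**Step 4: the same rule with b_1.** With two equal arms, SE(b_1) ≈ 2 × residual SD/√n; as a fraction of mean ALT this is 2 × 0.5/√70 = 0.120 and 2 × 0.5/√112 = 0.0945.
- True reduction 20%: the upper limit of a 95% interval lies above the true value in 97.5% of trials, whatever the variance. Simulated: about 97 to 98%.
- True reduction 40%: simulated 99.9 to 100%.
- True reduction 0%: the probability is about 1 − Φ(0.20/SE − t). For n = 70 this is 1 − Φ(1.673 − 1.996) = 63%; for n = 112 it is 1 − Φ(2.116 − 1.982) = 45%. Simulated: 43 to 65%. With a smaller residual SD of 0.375 × mean and n = 112, SE = 0.0709 and the result is 1 − Φ(2.822 − 1.982) = 20%. Across all variances tried, the simulated range was about 19 to 65%.

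**The case against.** The best defence is that this is a slip of labelling, not a wrong rule. The synopsis, section 3.3 and section 7.5 all say in words that the comparison is obeticholic acid against placebo, and only the symbol disagrees. An analyst would probably take the x_1 coefficient, and a limit below 4% that ignored the arms' mean changes would be noticed. That stands, and it makes harm unlikely. It does not make the formula right: the symbol is wrong in every expression, and the slip cannot be excused by counting the intercept as the first coefficient, because the model numbers from β0.

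Two stronger readings are tempting. A reader might infer that the continuation criterion can never be met. The documents do not support that, because what is written includes the verbal definition, under which it can be met. Even for the symbols alone the failure is practical, not algebraic (step 2). A reader might also infer that the trial would be stopped for an effective drug. Section 7.5 calls the rule a guideline used to advise NIDDK. The synopsis and section 7.6 leave the final decision to the NIDDK program official, who also weighs DSMB recommendations, safety and other information. The primary histological analysis does not use this formula.

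It is also fair to say that the simulation is not needed to establish the error. Reading the model is enough; the simulation only sizes the literal reading.

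**Conclusion.** The point holds as an error in a pre-specified decision formula. By the protocol's own model, b_2 is the wrong coefficient for the difference, its interval and standard error, the percentage and the limit tested against 20%. The existence of the error rests on no assumption.

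Its size does. For assumed baseline means of 50 to 110 U/L and the slopes and variances above, the literal limit is about 0.5 to 3%, far below 20% and unrelated to the drug effect. The practical risk is low, because the intended contrast is plain from the text and the rule is advisory.

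One further inference should be avoided: that the corrected formula is a demanding test of activity. Because it asks only that the upper limit reach 20%, it would be met in about 19 to 65% of trials with no true effect, depending on n and on the residual variance, which the protocol does not give. That leniency belongs to the rule's design and is separate from the coefficient error.

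**What to change.** In the paragraph of section 7.5 that follows the model, replace b_2 with b_1 everywhere:
- difference = b_1
- 95% CI = b_1 ± t(n−3) · SE(b_1)
- net reduction (%) = 100 · b_1 / mean baseline ALT
- upper limit (%) = 100 · [b_1 + t(n−3) · SE(b_1)] / mean baseline ALT

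Confirm that the PROC REG analysis takes the estimate and standard error for x_1. If the vanguard analysis has already been run, record which coefficient was reported to the DSMB. The cost is a subscript correction in one paragraph and a check of one program, with no effect on patients, data or sample size.
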